**APPENDIX I. EUROQOL-5D**

**Health Questionnaire**

**English version for the USA**

SAMPLE

Under each heading, please check the ONE box that best describes your health TODAY.

**MOBILITY**

- I have no problems walking
- I have slight problems walking
- I have moderate problems walking
- I have severe problems walking
- I am unable to walk

**SELF-CARE**

- I have no problems washing or dressing myself
- I have slight problems washing or dressing myself
- I have moderate problems washing or dressing myself
- I have severe problems washing or dressing myself
- I am unable to wash or dress myself

**USUAL ACTIVITIES** (e.g. work, study, housework, family or leisure activities)

- I have no problems doing my usual activities
- I have slight problems doing my usual activities
- I have moderate problems doing my usual activities
- I have severe problems doing my usual activities
- I am unable to do my usual activities

**PAIN / DISCOMFORT**

[figure not shown]
- I have no pain or discomfort
- I have slight pain or discomfort
- I have moderate pain or discomfort
- I have severe pain or discomfort
- I have extreme pain or discomfort

**ANXIETY / DEPRESSION**

- I am not anxious or depressed
- I am slightly anxious or depressed
- I am moderately anxious or depressed
- I am severely anxious or depressed
- I am extremely anxious or depressed

- We would like to know how good or bad your health is TODAY.
- This scale is numbered from 0 to 100.
- 100 means the best health you can imagine.  
0 means the worst health you can imagine.
- Mark an X on the scale to indicate how your health is TODAY.
- Now, please write the number you marked on the scale in the box below.

YOUR HEALTH TODAY =

**21. ADDENDUM**

Addendum A Substudy

## **ADDENDUM A. SUBSTUDY TO PROTOCOL ALK3831-A303 (FOR SELECTED SITES ONLY)**

### **Introduction and Rationale**

Weight gain is a well-documented side effect associated with olanzapine use (Eli Lilly and Company 2016) and thus is the primary efficacy measure in ALK3831-A303 (see Section 5.1 of the protocol). In addition to weight gain, changes to body composition (ie, increases in total fat mass and in visceral fat accumulation) have also been observed with olanzapine use in subjects with schizophrenia (Ader et al, 2008; Graham et al, 2005).

Bioelectrical Impedance Analysis (BIA) is a method of measuring body composition in which an electrical current is passed through the body and an impedance value is generated based on body height and the measured electrical conductance. Because fat mass and lean mass conduct electricity differently, the relative proportion of each tissue type can be derived from the impedance value (Ellis 2000).

Advancements in bioelectrical impedance technology allow for body composition measurements that can be collected uniformly across clinical trial sites without additional burden to the subjects in contrast to other methods such as dual-energy X-ray absorptiometry (DEXA) and magnetic resonance imaging (MRI). Using BIA, this substudy will evaluate body composition in a subset of subjects at a select number of sites participating in ALK3831-A303. As this is an exploratory substudy, body composition will be measured at two timepoints to provide data which may inform future studies.

### **Objective**

The objective of this exploratory substudy is to determine body composition during Visit 2 and at the end of treatment (Visit 17/ early termination [ET]) of subjects who are participating in study ALK3831-A303.

### **Selection of Subjects**

Eligible subjects who are at an ALK3831-A303 site participating in the substudy and who sign a separate consent will have these additional assessments collected if they meet the inclusion and exclusion criteria below.

### **Subject Inclusion Criteria**

Each subject must meet both of the following inclusion criteria to be qualified to participate in this substudy.

1. Enrolled in study ALK3831-A303 at a site equipped with a body composition analyzer
2. Consented to have body composition analysis conducted on or prior to Visit 2

## **Subject Exclusion Criteria**

Each subject must not meet the following criteria to be qualified to participate in this substudy.

1. Subjects with an electronic implant or devices of any kind (eg, pacemaker, infusion pump) or any active or powered prostheses.

## **Subject Withdrawal**

Subjects may withdraw consent from participation in this substudy at any time. If they do so, they may continue full participation in the main ALK3831-A303 study.

## **Substudy Design**

The substudy will be conducted in up to 200 subjects participating in the main ALK3831-A303 study. The substudy will be completed in conjunction with the main study protocol. Subjects who enroll in the substudy will complete all the study procedures described in the main study protocol (see [Table 1](#)). Additionally, subjects in the substudy will have a body composition assessment done prior to dosing at Visit 2 (confirmation of eligibility and randomization visit) and then again upon completion of the study at Visit 17/ET (see [Table 1](#)).

**Table 1: Substudy Schedule of Assessments**

Visit	Screening Day -30 to -1	24-Week Double-Blind Treatment															Safety Follow- up		Monthly Visits	
	1	2	3	4	5	6	7	8	9	10	11	12	13	14	15	16	17/ ET	18	19	20 to 24
Study Week (Visit Window of ±2 Days for Visits 3-24)			1	2	3	4	5	6	8	10	12	14	16	18	20	22	24	26	28	
Consent for Substudy	X	X a																		
Body Composition Assessment		X															X			

Abbreviation: ET=early termination

a If not consented at Visit 1, subjects may be consented at Visit 2 prior to any assessments.

## Body Impedance Analysis Procedure

Body composition will be assessed using the Seca Medical Body Composition Analyzer (mBCA 514). For the body composition measurements, subjects should be asked to void immediately prior to measurement and should be dressed in a hospital gown with consistent under-attire for each measurement. Subjects should remove all personal items (including shoes, watches, and jewelry) and they should be standing on the same scale for each measurement under the same condition. At timepoints when body composition is measured, subjects will be asked to stand on the two separate study-supplied scales. The body composition analysis should not be performed when the subject is attached to any portable electronic equipment (eg, a portable electrocardiogram machine).

## Substudy Exploratory Endpoints

This substudy will assess the following exploratory endpoints:

- Absolute change from baseline in lean mass
- Absolute change from baseline in fat mass
- Change from baseline in percent body fat

## Statistical Analysis

The analysis will be carried out using ANCOVA (analysis of covariance) model with treatment group, race (Black or African American, Non-Black or African American), and baseline age (<30, ≥30 years) as factors, and the baseline value as the covariate. Please refer to the statistical analysis plan (SAP) for analysis details. Results from the substudy will be provided in an addendum, which will be included as an appendix of the main ALK3831-A303 clinical study report.

## Safety Reporting

Adverse events and serious adverse events will be captured and reported in accordance with the main ALK3831-A303 study ([Section 13](#) of the protocol).

## Informed Consent

A separate informed consent will be obtained from subjects who voluntarily agree to participate in the BIA substudy. The Informed Consent Form reflecting this substudy will be submitted for review and approval to the responsible Institutional Review Board (IRB).

## Institutional Review Board

The Informed Consent Form for this substudy will be submitted for review and approval to the IRB charged with this responsibility.

PANSS	Positive and Negative Syndrome Scale
PCS	potentially clinically significant
PK	pharmacokinetic
QTcB	QT corrected with Bazett formula
QTcF	QT corrected with Fridericia formula
SAE	serious adverse event
SAP	statistical analysis plan
SAS	Simpson-Angus Scale
TEAE	treatment-emergent adverse event
ULN	upper limit of normal
WHO	World Health Organization

1. INTRODUCTION

This statistical analysis plan (SAP) describes the statistical methods to be used for analyses and data presentation for reporting efficacy and safety results for study ALK3831-A303. This document has been prepared based on Alkermes [ALK3831-A303 Study Protocol](#).

1.1. Study Objectives

Primary objective:

- To evaluate weight gain of ALKS 3831 (a fixed-dose combination of olanzapine and samidorphan) compared to olanzapine in adults with schizophrenia

Secondary objective:

[figure not shown]
- To evaluate the safety and tolerability of ALKS 3831 in adults with schizophrenia

1.2 Summary of the Study Design

This is a Phase 3, multicenter, randomized, double-blind, study in adults with schizophrenia.

Subjects will be screened at Visit 1, up to 30 days prior to randomization. At Visit 2, eligible subjects will be randomized 1:1 to ALKS 3831 (olanzapine/10 mg samidorphan) or olanzapine treatment groups and receive study drug for up to 24 weeks. Subjects are not excluded from the study if they are taking other antipsychotic medication. However, they must be tapered off this medication and switched onto ALKS 3831 or olanzapine by the end of Week 2, Visit 4. This is an outpatient study in which subjects will visit the study site weekly for the first 6 weeks, then biweekly for the remaining 18 weeks. Study drug will be provided as coated bilayer tablets dispensed to the subjects in blister packs at each visit to be taken at home, one tablet by mouth each day, preferably at bedtime. For the first week, subjects will receive 10 mg olanzapine per dose: either ALKS 3831 10/10 (10 mg olanzapine/10 mg samidorphan) or OLZ 10 (10 mg olanzapine), according to treatment assignment. At the end of Week 1, the dose will escalate to 20 mg: ALKS 3831 20/10 [20 mg olanzapine/10 mg samidorphan] or OLZ 20). Following this increase, the dose may be decreased back to 10 mg at the end of Week 2, 3, or 4 according to investigator discretion. No further dose adjustments will be allowed beyond Week 4 and the dose will remain fixed for the remaining 20 weeks of the study. Body weight and metabolic parameters (including fasting triglycerides, cholesterol, and glucose) will be measured throughout the 24-week treatment period. Psychiatric symptoms will also be evaluated using Positive and Negative Syndrome Scale (PANSS) and Clinical Global Impression (CGI). A schematic summarizing study design is presented below.

Figure 1: ALK3831-A303 Study Design Schematic

Subjects completing this study will be eligible to enroll in a long-term safety study (ALK3831-A304). Subjects not continuing in the long-term safety study or subjects prematurely discontinuing from the study will enter the 4-week safety follow-up period.

Premature discontinuation procedures are provided in [Protocol Section 7.3](#). Randomized subjects who discontinue study drug but are willing to come in for further assessments will be asked to complete the early termination (ET) visit followed by 2 safety follow-up visits 2 and 4 weeks after the ET visit. They will then be asked to return to the study center for monthly visits until end of planned treatment, to collect the following information: weight, adverse events, and new antipsychotics.

2. SAMPLE SIZE CONSIDERATION

The initial target sample size is 200 randomized subjects per treatment group (400 in total). This sample size will provide at least 90% power to detect a significant difference in mean percent change in body weight at Week 24 of 4% or more (3.0% on ALKS 3831 versus 7% on olanzapine group with standard deviation of 9%) and a 13% difference in proportion of subjects with $\geq 10\%$ weight gain at Week 24 (14% on ALKS 3831 versus 27% on olanzapine group).

An unblinded interim analysis is planned to be conducted to determine if the final sample size will be increased to 540 (270 subjects per treatment group), details in [ALK3831-A303 Interim Analysis Plan](#).

3. DATA ANALYSIS

3.1. General Statistical Methodology

Baseline for the primary efficacy or safety analysis is defined as the last non-missing efficacy or safety assessment before the first dose of double-blind study drug.

In general, descriptive statistics: n, mean, standard deviation (SD), median, minimum, and maximum, for continuous variables and number and percentage of subjects in each category for categorical variables will be provided by treatment group for all variables.

The fasting lipids and fasting glucose laboratory parameters will be analyzed on a linear and log-transformed scale.

All statistical tests and confidence intervals (CIs), unless stated otherwise, will be 2-sided and will be set at an alpha level of 0.05.

To adjust for the unblinded interim analysis for sample size re-estimation, the CHW method will be applied to the primary analysis of the two primary endpoints only, with details in [Section 3.8.2.1.1](#) and [Section 3.8.2.2.1](#). It will not be applied to the sensitivity or additional analysis of the two primary endpoints, analysis of the key secondary, other, exploratory endpoints, or subgroup analyses.

All source data will be presented as subject data listings.

Body weight is measured 3 times at every visit. The median weight will be used in summary tables or figures.

3.2. Definitions of Analysis Populations

3.2.1. Safety Population

The Safety Population includes all randomized subjects who receive at least 1 dose of study drug (ALKS 3831 or olanzapine). The Safety Population will be used for the safety analyses.

3.2.2. Efficacy Population

The Full Analysis Set (FAS) includes all subjects in the Safety Population who have at least one postbaseline weight assessment. The FAS will be used for the efficacy analyses, unless specified otherwise.

The Early Weight Gain population includes all subjects in the FAS population who gain weight (>0 kg) at Week 1.

Stage 1 Subjects are defined as first 200 FAS subjects who have completed or prematurely discontinued before the interim analysis.

Stage 2 Subjects are defined as FAS subjects who completed or prematurely discontinued after the interim analysis.

3.3. Disposition

The number and percentage of subjects completing or prematurely discontinuing the study including reasons for discontinuation will be summarized overall and by treatment group for the following.

- Subjects who were randomized
- Subjects in the Safety Population
- Subjects in the FAS Population
- Subjects in the Early Weight Gain Population
- Subjects who completed the double-blind treatment period

- Subjects who discontinued the study during the double-blind treatment period along with reasons for discontinuation

3.4. Demographics and Baseline Characteristics

Demographics and baseline characteristics such as sex, age, race, ethnicity, weight, and body mass index (BMI) and psychiatric history will be summarized overall and by treatment group for the Safety Population, the FAS Population, and the Early Weight Gain Population. If there are heterogeneities between study groups in any of the subject characteristics that are of clinical importance or could affect the treatment outcome, the impact of the imbalances will be investigated and, if necessary, appropriate adjustments made in the efficacy and safety analyses.

Medical history will be summarized for the Safety Population by treatment group and overall using the number of observations and percentage of subjects reporting each category.

3.5. Protocol Deviation

Subjects with major protocol deviations in the following categories will be summarized by treatment group along with supportive listings for each category.

- Did not meet the inclusion/exclusion criteria
- Received prohibited medications
- Lack of adherence with study medication, as defined by subjects taking less than 70% of the protocol-specified amount of study medication
- Randomization or dosing error

3.6. Prior and Concomitant Medication

Prior medications are defined as medications taken prior to the first dose of study drug. Concomitant medications are defined as medications taken on or after the first dose study drug. All medications as documented by the investigator will be coded using the World Health Organization Anatomical Therapeutic Chemical (WHO-ATC) drug dictionary Enhanced Extended with Herbal version WHODRUG_C / 161E+H.

Prior and concomitant medications will be summarized by the preferred drug name for the Safety Population. Concomitant medications that are taken during the double-blind treatment period will be included in the summary table. For subjects who discontinue study drug prematurely and return for monthly visits, all antipsychotic medications that are taken after the last dose of study medication will be summarized separately. For the summary tables, if a subject has taken a prior or concomitant medication more than once, the subject will be counted only once for the medication. All reported medications (including those initiated after the last dose of double-blind study medication) will be included in the listing.

3.7. Treatment Adherence Rate and Extent of Exposure

3.7.1. Treatment Adherence Rate

Treatment adherence to the daily dosing schedule during the double-blind treatment period will be summarized by treatment group for the Safety Population. Treatment adherence will be calculated as follows:

$$100 \times \frac{\text{Total tablets dispensed} - \text{total tablets returned} - \text{total tablets lost}}{\text{Total tablets scheduled to be taken}}$$

3.7.2. Duration of study drug administration

Duration of study drug administration (ALKS 3831 and OLZ) is defined as the number of days from the date of the first dose of study drug taken to the date of the last dose taken, inclusive (ie, last dose date – first dose date + 1). Duration of study drug administration will be summarized for the Safety Population by treatment group.

The overall mean and modal dose of olanzapine will be summarized by treatment group. Number and percentage of subjects will be summarized by their Visit 6 (Week 4) dose level and by final dose level.

3.8. Efficacy Analyses

3.8.1. General Considerations

All statistical tests will be 2-sided hypothesis tests performed at the 5% significance level. All confidence intervals will be 2-sided 95% confidence intervals.

Baseline for the primary efficacy analysis is defined as the last non-missing observation on or before the first dose of study drug in the double-blind treatment period.

Only the on-treatment weight assessments will be included in the analyses, unless specified otherwise.

3.8.2. Primary Efficacy Endpoints

The primary efficacy endpoints are

- percent change from baseline in body weight at Week 24 in FAS population
- proportion of subjects with $\geq 10\%$ weight gain at Week 24 in FAS population

3.8.2.1. Primary Efficacy Endpoint: Percent Change from Baseline in Body Weight at Week 24 in the FAS population

3.8.2.1.1. Primary Analysis

The primary endpoint will be analyzed by analysis of covariance (ANCOVA) with the multiple imputation (MI) method for handling of missing values. Only the on-treatment measurements will be included in the analysis. The following steps will be performed:

1. The missing data on body weight in Stage 1 subjects will be imputed using MI. If there is any subject whose missing data pattern is non-monotonic (defined as having missing data in between visits), the Markov Chain Monte Carlo (MCMC) method will be used to impute the data to a monotonic missing pattern (i.e., if the data is missing at the current visit, the data at all following visits are missing). A single Markov chain will be used with 200 burn-in iterations, 100 iterations between imputations and a Jeffrey's prior. Next, the missing data will be imputed sequentially by each visit using a regression method. The imputation regression model includes treatment group, race (Black or African American, Non-Black or African American) and baseline age (<30, ≥30 years) as factors, and body weight at all previous visits (including baseline weight) as covariates. At least five hundred imputations will be carried out. More imputations may be performed to improve the precision. The initial seed for both steps of the imputation will be 1104078.
2. Percent change from baseline in weight at Week 24 of each of these multiply imputed datasets will be analyzed by the ANCOVA model with treatment group, race (Black or African American, Non-Black or African American), and baseline age (<30, ≥30 years) as factors, and the baseline weight as covariate.
3. Results from Step 2 will be combined using Rubin's method to get the Stage 1 results, including estimated treatment effect, standard error and test statistic z_1 .
4. Repeat Steps 1 to 3 for Stage 2 Subjects. Estimated treatment effect, standard error and test statistic z_2 will be obtained.
5. To adjust for the IA for sample size re-estimation, the independent test statistic from two stages will be combined using the CHW method with a fixed weight of $\sqrt{0.5}$ based on the original sample size (Cui et al, 1999):

$$Z_{chw}^* = \sqrt{t_1}z_1 + \sqrt{1 - t_1}z_2$$

where $t_1 = 200/400$,

In addition, to estimate the treatment effect, the same MI procedure will be performed based on the entire dataset including all FAS subjects. Five hundred imputations will be carried out. The results will be analyzed by the same ANCOVA model and combined using Rubin's method. Estimated treatment effect, standard error (SE), and 95% CIs will be reported.

Descriptive statistics of body weight and percent change from baseline at each visit (including last assessment during treatment period) will be presented by treatment group based on observed and MI-imputed data.

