3.8.2.2.1. Primary Analysis

The primary analyses will be carried out using a logistic regression model based on MI for missing data as described in Section 3.8.2.1.1. Proportion of subjects with ≥10% Weight Gain at Week 24 will be derived based on the same complete datasets obtained from the multiple imputation procedure. The logistic regression model will include the treatment group, race (Black or African American, Non-Black or African American), and age (<30, ≥30 years) as factors; and the baseline weight as the covariate. For subjects who prematurely discontinue the study drug but are willing to come back for weight assessments, only on-treatment weight assessments will be included in the primary analyses.

Similarly to the primary efficacy endpoint of percent change from baseline body weight at Week 24, the independent test statistic before and after the interim analysis will be combined using the CHW method with a fixed weight of $\sqrt{0.5}$ based on the original sample size. The treatment effects and 95% CIs will be reported as described in Section 3.8.2.1.1.

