3.8.4. Multiple Comparison/ Multiplicity

The study will be claimed positive when the primary analyses of both co-primary efficacy endpoints are statistically significant based on the CHW method to adjust for the unblinded interim analysis for sample size re-estimation; therefore, both co-primary endpoints will be tested at a full α level of 0.05. A fixed sequence approach will be used to control overall Type I error rate for the primary and key secondary endpoints. Only if both primary endpoints are statistically significant based on the CHW method will the key secondary endpoint be further tested at an alpha level of 0.05.

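### If the trial grows to 540, the CHW test and the only planned 95% CI weight the two stages differently, so borderline results can conflict in either direction, and no CI matching the test is planned

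*SAP*

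**What the plan says.** **Test.** SAP 3.8.2.1.1 (steps 1 to 5) imputes and analyses Stage 1 and Stage 2 separately. It then combines z1 and z2 with fixed weights of √0.5 each, whatever the final sample size. SAP 3.8.2.2.1 does the same for the proportion with ≥10% weight gain. SAP 3.8.4 makes this the sole criterion: "The study will be claimed positive when the primary analyses of both co-primary efficacy endpoints are statistically significant based on the CHW method".

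**Estimate and interval.** SAP 3.8.2.1.1 continues that, to estimate the treatment effect, "the same MI procedure will be performed based on the entire dataset including all FAS subjects". The estimate, SE and 95% CI come from that single fit, with no stage weights. For the ≥10% endpoint, "The treatment effects and 95% CIs will be reported as described in" the same section. SAP 3.8.1 adds: "All confidence intervals will be 2-sided 95% confidence intervals".

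**Adaptation.** SAP 2 and SAP 4 (also Protocol 14.1 and 14.7) allow an increase from 400 to 540 after an unblinded look at 200 subjects. The increase follows if at least one endpoint has conditional power of 30% to below 90% and neither is below 30%. Neither document says under which effect conditional power is computed. The testing methodology is referred to the interim analysis plan.

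SAP 3.1 sends the reader to 3.8.2.1.1 and 3.8.2.2.1 for the CHW details. Neither gives an interval that matches the test, or says what to report if test and interval disagree.

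**The concern.** A reader expects a 95% CI to exclude no effect exactly when the accompanying two-sided 5% test is significant. SAP 3.1 invites that expectation by setting tests and intervals at the same alpha: "All statistical tests and confidence intervals (CIs), unless stated otherwise, will be 2-sided and will be set at an alpha level of 0.05". Here the interval inverts a different statistic from the one that decides the trial. It is also computed as though the sample size had been fixed in advance.

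At stake is how a borderline co-primary result is read. A positive endpoint could be published with a CI that includes zero (or an odds ratio of 1), or a failed endpoint with a CI that excludes it. Without a pre-specified matching interval, the choice between two presentations would be made after the result is known.

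**Working it through.** **1. Reproduce the plan's own figure.** The inputs from SAP 2 are 200 per arm, 3% vs 7% with SD 9, and 14% vs 27%. For these the plan states: "This sample size will provide at least 90% power".

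- Percent change: expected z = 4/(9·√(2/200)) = 4.44, so power = Φ(4.44 − 1.96) = 99.4%.
- ≥10% gain: expected z = 0.13/√((0.14·0.86 + 0.27·0.73)/200) = 3.26, so power = Φ(3.26 − 1.96) = 90.4% (89.9% with pooled variance).

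The stated power is reproduced. The ≥10% endpoint is the one near the boundary.

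**2. Weights.** Stage 1 has 200 subjects. Stage 2 has 200, or 540 − 200 = 340 after an increase.

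- Test: Z_chw = 0.707·z1 + 0.707·z2 in both cases.
- Pooled fit at 400: √(200/400) = 0.707 for each stage, identical to the test.
- Pooled fit at 540: √(200/540) = 0.609 and √(340/540) = 0.793.

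**3. Where they part.** On the boundary Z_chw = 1.96, z2 = 2.772 − z1. The pooled Z at 540 is then 2.200 − 0.185·z1, which is below 1.96 when z1 > 1.295 and above it when z1 < 1.295. At the boundary the pooled p is 0.055 for z1 = 1.5 and 0.067 for z1 = 2.0.

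**4. Is this reachable?** Taking conditional power (CP) against the original 400:

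- Current-trend CP = Φ((1.414·z1 − 1.96)/0.707). The promising zone is z1 = 1.124 to 2.027, mostly above 1.295.
- Design-effect CP for the ≥10% endpoint = Φ((0.707·z1 + 0.5·3.26 − 1.96)/0.707). The zone is z1 = −0.06 to 1.75, mostly below 1.295.

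Both zones straddle 1.295, so both kinds of conflict can occur. The unseen CP definition decides which is commoner.

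**5. One worked case** (percent change, SD 9, 540 subjects, z1 = 2.00, z2 = 0.80).

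- SE1 = 18/√200 = 1.273 and SE2 = 18/√340 = 0.976. The stage effects are 2.546 and 0.781.
- Z_chw = 0.707·2.80 = 1.980, p = 0.048: significant.
- Pooled: (200·2.546 + 340·0.781)/540 = 1.43, SE = 18/√540 = 0.775, 95% CI −0.08 to 2.95 (p = 0.064). It includes zero.
- Inverting Z_chw: I = 0.707/1.273 + 0.707/0.976 = 1.280. Estimate = 1.980/1.280 = 1.55, 95% CI 0.02 to 3.08. It agrees with the test.
- Ratio of SEs: (1/1.280)/0.775 = √540/(√100 + √170) = 1.009.

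**6. How often.** These results are from simulation of the documented increase rule with two correlated endpoints. Correlation 0.7 is assumed; 0.5 and 0.9 change little at the planned effects. The z-statistics are taken as normal, with no missing data.

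| | Current-trend CP | Design-effect CP |
|---|---|---|
| ≥10% endpoint, planned effects, given an increase: CHW significant, CI includes no effect | 0.4–0.5% | 0.2% |
| Same, reverse: CHW not significant, CI excludes no effect | 0.03–0.04% | 1.4–1.5% |
| All trials, planned effects: study positive, at least one CI includes no effect | 0.12–0.13% | 0.06% |
| All trials, half the planned effects: same event | 0.9% | 0.4% |
| All trials, half the planned effects: study fails, both CIs exclude no effect | 0.05% | 2.0% |

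Coverage of the pooled CI across scenarios is 94.5% to 95.1%. The interval from inverting Z_chw has 95.0%.

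**The case against.** The strongest reply is that the SAP separates testing from estimation on purpose. SAP 3.1 confines CHW to the primary analysis of the two primary endpoints. SAP 3.8.2.1.1 presents the pooled fit as the means of estimating the effect. SAP 3.8.4 leaves no doubt that CHW alone decides the trial. The pooled estimate gives every subject equal weight, whereas the CHW-based estimate down-weights Stage 2 subjects when 340 follow 200. Each stage's effect and SE are planned output, so anyone could derive the matching interval later.

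Most of this stands. The decision rule is unambiguous, the pooled estimate is a legitimate choice, and this is a reporting improvement, not the correction of an error. What it does not answer is that no interval matching the test is pre-specified, and nothing says how a conflict would be presented.

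Three stronger readings are tempting, and the documents do not support them:

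- *Conflicts would nearly always be a significant test with a CI that includes no effect.* That holds under current-trend CP only. Under design-effect CP the reverse dominates by about 1.5% to 0.2%.
- *The pooled CI materially under-covers.* SAP 4 claims type I error control for the CHW statistic, and that argument does not extend to the pooled interval. Even so, simulated coverage falls no lower than 94.5%.
- *Type I error is at risk.* It is not, because the pooled CI has no part in the decision.

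**Conclusion.** The point holds as a minor one. After an increase to 540, test and interval rest on different stage weights and can disagree in either direction for borderline results. The planned analysis offers no interval consistent with the test. If the trial stays at 400 the issue essentially vanishes; small departures of the FAS counts from 200 per stage leave only a trace of it.

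A positive study with a conflicting interval would be rare: about 1 in 1,000 trials or fewer at the planned effects and under 1% at half of them. The reverse conflict could reach about 2% of trials at half the planned effects under design-effect CP.

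The existence of the mismatch follows from the SAP's own weights. Its frequency and main direction rest on assumptions the documents do not settle: the CP definition, the correlation between endpoints, and the absence of missing-data variance. The interim analysis plan was not available and may contain an adjusted interval. SAP 3.1, however, points to the SAP's own sections for the CHW details.

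**What to change.** In SAP 3.8.2.1.1 and 3.8.2.2.1, report beside each CHW p-value the estimate and 95% CI obtained by inverting Z_chw:

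- I = √0.5/SE1 + √0.5/SE2
- estimate = Z_chw/I
- 95% CI = (Z_chw ± 1.96)/I

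For the ≥10% endpoint, work on the log-odds scale and exponentiate. State that this is the interval that accompanies the test. Keep the pooled MI estimate and CI, labelled as unadjusted for the sample-size adaptation.

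The stage-specific effects, SEs and z-values already come out of steps 3 and 4 of the primary analysis, so this needs a few lines of code and changes no test, alpha or decision rule. The downside is a CI about 0.9% wider at 540, and two intervals per co-primary endpoint that must be clearly labelled.
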